3.0 Purpose and Objectives

The purpose of the Evaluation of Factors Affecting Clinical Outcome and Cost Effectiveness of the S-ICD or "EFFORTLESS S-ICD" Registry, is to document early, mid-and long-term operational and clinical outcomes associated with the implantation of the Boston Scientific S-ICD system. The evaluation will include documenting the patients' perception of his/her therapy through Quality of Life (QOL) assessments. The study will be conducted at approximately 50 clinical centres worldwide in patients requiring an ICD for the treatment of ventricular tachyarrhythmias.

Data will be collected to evaluate perioperative (30 day post implant), mid- (360 day post implant) and long-term (up to 60 months) clinical complication rates associated with the implantation of the S-ICD system as well as the percentage of patients experiencing inappropriate shocks for AF and/or SVT. The Registry will also include analysis of resource utilization and costs based on measures of clinical outcome such as complication rates, unscheduled hospitalizations and length of stay. The objective will be to enable comparison of costs of the S-ICD system versus a standard transvenous system.

The Sub-Study (see Appendix E) will extend the EFFORTLESS S-ICD Registry in order to collect long-term follow-up data on a subset of EFFORTLESS patients to achieve an average of approximately 8 years of follow-up from index procedure.

The purpose of the Sub-Study is to document the reason for S-ICD system replacements or revisions and describe the associated clinical events and outcomes.

Data will be collected in conformance with the "Declaration of Helsinki", ISO 14155:2009 and the laws and regulations of the country in which the research is conducted.

3.1 Registry Objective

The objective of the EFFORTLESS S-ICD Registry is an observational, standard of care evaluation designed to demonstrate the early, mid and long-term clinical effectiveness the Boston Scientific S-ICD System. In addition, analysis of resource utilization and costs will be performed to document treatment costs for periods defined by Registry endpoints.

3.2 Registry Endpoints

The primary Registry endpoints will be examined using the following metrics:

- **Registry Endpoint 1:** Perioperative (30 days post implant) S-ICD System Complication Free Rate

Boston Scientific
EFFORTLESS S-ICD Study Protocol
90904925, Rev/Ver AB

Page 14 of 52

- **Registry Endpoint 2:** 360 day S-ICD System Complication Free Rate
- **Registry Endpoint 3:** Percentage of Inappropriate Shocks for AF/SVT

3.2.1 Observational Data Collection

When available, descriptive statistics will be used to present observational data to further characterize the performance of the S-ICD system. This can include (but is not limited to):

- Clinical Indications for implant
- Patient demographics
- Type of anesthesia/analgesia
 - General anesthesia/local anesthesia/conscious sedation etc.
- Implant procedure duration
- Use of fluoroscopy and X-Ray
- Induced Shock Conversion Efficacy
 - Defined as any shock delivered by the S-ICD pulse generator that terminates the induced arrhythmia and does not require an external defibrillator.
- Spontaneous Shock Conversion Efficacy
 - Defined as any shock delivered by the S-ICD pulse generator that terminates the spontaneous arrhythmia (device defined end of episode)
- First Shock Conversion Efficacy
 - Defined as the percentage of successful conversions (device defined end of episode) caused by the first shock delivered by the S-ICD pulse generator. Data will be evaluated for both induced and spontaneous episodes
- All cause therapy (appropriate and inappropriate)
 - Inappropriate therapy is defined as delivery of shock therapy for any rhythm other than VT/VF.
- Total Shock Burden
 - Defined as the total number of therapies delivered (both appropriate and inappropriate) divided by the total number implanted patients
- Complication rates over time
- Frequency of scheduled and unscheduled follow-ups/hospitalizations
- All cause mortality
- Length of hospital stay
 - Where possible, hospital stay lengths will be calculated for implant procedure as well as scheduled and unscheduled follow-ups

- All clinical events
- Clinical event rates over time
- QOL Assessments
 - Patients will complete a brief set of standardized QOL questionnaires at baseline (pre-implant), 3 months post-implant, 6 months post-implant and 12-months post implant (see section 7.8) with the intention of comparing scores with a transvenous ICD cohort
- Hospital personnel implant and Follow-Up Experience (using an optional survey to be completed at two time points)

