Design:	
EFFORTLESS S-ICD is an observational, prospective, non-randomized Registry that will be conducted at approximately 50 clinical centres worldwide. Approximately 1000 patients implanted with, or meeting eligibility criteria for the implantation of the S-ICD system will be enrolled and followed per standard of care for up to 60 months post implant.
	
Primary Objective:	
To demonstrate the early, mid- and long-term clinical outcome of the S-ICD system.
	
Registry Endpoints	
 • Perioperative (30 days post implant) Complication-Free Rate • 360-day Complication-Free Rate • Percentage of Inappropriate Shocks for AF/SVT 	
Observational Data Collection	
 • Clinical Indications for implant • Patient demographics • Type of anesthesia/analgesia • Implant procedure duration • Use of fluoroscopy and X-Ray • Shock conversion efficacies (spontaneous & induced) • All cause therapies (appropriate & inappropriate) 	
 • Overall complication rates with time • Frequency of scheduled/unscheduled follow-ups/hospitalizations • All cause mortality • Length of hospital stay (implant procedure and follow-ups) • All clinical events • Clinical event rates over time • Quality of Life

	
 Total shock burden 	
 Hospital personnel implant and follow-up experience (using surveys)
Sample Size:	The target sample size is approximately 1000 patients.	
Registry Duration:	The expected duration, from enrolment to closure of the main Registry, will be approximately 108 months.	
Patient Selection:	Patients from the investigators' general implantable cardioverter-defibrillator (ICD) patient population will be eligible to be enrolled in this Registry. Patients should meet all the inclusion criteria and none of the exclusion criteria. Retrospective enrolments are allowed providing minimal data requirements are met.	

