5.0 Statistical Methods and Analysis

The statistical analyses related to this Registry including the Sub-Study (see Appendix E) will be executed by the Boston Scientific Clinical Department and/or consultants working on behalf of Boston Scientific. All patients enrolled in the Registry will be included in the analysis. As an observational non-randomized single arm evaluation, the statistical analyses will be descriptive.

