5.5 Additional Data Analysis

- Conversion efficacies for both induced and spontaneous episodes and first shock will be summarized as the number of subjects and the percentages relative to the Registry population including the corresponding 95.0% two-sided exact binomial confidence interval.
- Clinical event rates will be presented as 30-day event rates as summarized by number of subjects and its corresponding percentage and 95.0% two-sided exact binomial confidence interval and long-term rates as either linear rates or Kaplan-Meier freedom from event.
- Linearised rate of inappropriate therapies will also be calculated by dividing the total number of inappropriate therapies by the total number of follow-up patient years. Linearised rate calculation will only be initiated if a minimum of 100 patient years have been reached.
- Kaplan-Meier estimates and curves for therapy delivered including:
 - Time to first therapy delivered (both appropriate and inappropriate)
 - Time to first appropriate therapy delivered
 - Time to first inappropriate therapy delivered
- Re-occurrence of inappropriate shock therapy after reprogramming will be calculated using the total number of additional inappropriate shocks recorded from patients who have previously experienced at least one inappropriate shock and had their S-ICD reprogrammed in an attempt to resolve the issue (adjustments may include but are not limited to, changing sensing vector, adjustment to ECG gain, reprogramming of shock rates)
- Considering that patients who are prospectively enrolled in this Registry will come from the investigator's general ICD population, it is a priori unknown how many will be primary versus secondary prevention patients. Analyses will be conducted for primary versus secondary prevention, for inclusion in separate cost-effectiveness models for those populations.

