7.3.2 Acute Defibrillation Testing

After implanting the S-ICD System, a ventricular arrhythmia can be induced using the S-ICD pulse generator, a temporary endocardial pacing catheter, or an alternative induction method at the discretion of the investigator. If conversion testing is performed during the initial implant procedure (or at any subsequent follow-up-scheduled or unscheduled) the following definitions will be applied to the testing with respect to data collected on the case report form:

- A *successful conversion* is defined as any shock delivered by the S-ICD pulse generator that terminates the induced VT/VF arrhythmia (device declared end of episode) and does not require an external defibrillator. This includes episodes where VT/VF converts but an atrial tachyarrhythmia may persist.
- A *failed conversion* is defined as the need for an external defibrillator following the inability of the S-ICD pulse generator to convert the VT/VF arrhythmia.
- An *attempt* is defined as an induction resulting in VT/VF that does not receive therapy (most probably due to the rhythm breaking prior to delivery of shock) and/or an induction not resulting in VT/VF.

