- Scan for devices, resulting in a display of pick list of S-ICD devices
- Establishment and termination of communication link
- Display of a real-time S-ECG
- Selection of programmable parameters
- Review of patient event history

S-ICD System Sensing and Detection

Prior to the commencement of sensing and detection of normal sinus rhythm (NSR) and/or arrhythmic events, Sensing Setup must be performed. This setup procedure may begin once the S-ICD pulse generator and subcutaneous electrode are implanted and connected.

The S-ICD System incorporates three possible sensing vectors: (1) Primary; (2) Secondary; and (3) Alternate. A Vector Selection algorithm is designed to automatically select the best sensing vector from the available vector choices. The algorithm measures critical components of the S-ECG signal and determines the best vector through analysis of signals recorded through these components. A Sense Vector Optimization algorithm is designed to incorporate the effect of posture into the vector selection algorithm.

The optimization is skipped during the implant procedure when positioning the patient in multiple postures is not practical. However, when utilized post-implant, the optimization algorithm will evaluate changes in sensing qualities that result from patient posture changes. A Reference ECG Acquisition (Template Formation) algorithm is designed to store the morphology of the patient's ECG during normal sinus rhythm. This template is later used while the S-ICD System continuously monitors the subcutaneous ECG for any tachyarrhythmia events.

Defibrillation Therapy

Once a defibrillation shock is deemed necessary, the pulse generator charges and up to 5 maximum energy (80 J) shocks are delivered for each episode. The defibrillation waveform is a truncated exponential, 50% tilt, biphasic waveform delivered between the pulse generator and the subcutaneous electrode coil. With the exception of shocks delivered manually or during induction testing, shock energy level is non-programmable and set to the maximum (80 J) output. The S-ICD System attempts to deliver all shocks synchronously with a detected cardiac event. An Adaptive Shock Polarity algorithm is designed to automatically select the polarity for the first shock delivered, based on the polarity of the last delivered successful shock. The algorithm will automatically alternate shock polarity for any necessary subsequent shocks.

Post-Shock Pacing

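### First Shock Conversion Efficacy has conflicting denominators in Sections 3.2.1 and 5.5, and neither gives the share of shocked VT/VF episodes ended by the first shock

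*Combined protocol and SAP*

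**What the plan says.** Section 3.2.1 lists First Shock Conversion Efficacy among the observational data: "Defined as the percentage of successful conversions (device defined end of episode) caused by the first shock delivered by the S-ICD pulse generator". It adds: "Data will be evaluated for both induced and spontaneous episodes".

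Section 5.5 says how the conversion efficacies are to be analysed. For induced episodes, spontaneous episodes and the first shock alike, the instruction is this: "first shock will be summarized as the number of subjects and the percentages relative to the Registry population". An exact binomial interval at the 95% level is to go with each percentage.

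Two other places bear on the meaning. Section 7.3.2 treats successful conversion, failed conversion and attempt as separate categories for induced testing. Of the failed category it says that it "is defined as the need for an external defibrillator following the inability of the S-ICD pulse generator to convert the VT/VF arrhythmia". Appendix A, under Defibrillation Therapy, says that "up to 5 maximum energy (80 J) shocks are delivered for each episode", so an episode can be converted by a later shock after the first has failed, or not be converted at all.

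**The concern.** A reader expects first-shock efficacy to answer one question: of the VT/VF episodes that the S-ICD shocked, how many ended with the first shock? Neither section asks it.

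Under the literal wording of 3.2.1 the base is successful conversions. An episode in which every S-ICD shock fails is in neither the numerator nor the denominator, so the measure does not register a complete failure. Under 5.5 the base is the whole Registry population. A patient who was never induced and never had a shocked arrhythmia cannot be a success, yet stays in the denominator.

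The two rules also differ in unit (conversions against subjects), and 5.5 does not say how to classify a subject whose first shock worked in one episode and failed in another. The same data could therefore produce very different percentages under one name. None of the three Registry endpoints in Section 3.2 measures arrhythmia termination, so the conversion efficacies are the Registry's direct evidence on that function.

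**Working it through.** **Plan's own figure.** The documents state no expected value or precision for first-shock efficacy, so there is nothing to reproduce for this measure. As a check on the interval method only, the exact (Clopper-Pearson) interval reproduces four cells of Table 1 in Section 5.6: 90% with n = 900 (-2.1/+1.9), 95% with n = 500 (-2.3/+1.7), 99% with n = 100 (-4.4/+1.0) and 90% with n = 100 (-7.6/+5.1).

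**Inputs from the documents.** The two denominators are as quoted. On the population, Section 5.0 says "All patients enrolled in the Registry will be included in the analysis", and on size the synopsis says "The target sample size is approximately 1000 patients". All conversion rates below are assumptions, because the documents give none.

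**Notation.** T = shocked VT/VF episodes; F = episodes converted by the first shock; C = episodes converted by any S-ICD shock; u = (T - C)/T; N = Registry population.

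**Rule in 3.2.1, read literally.** The figure is F/C. Since C = T(1 - u), F/C = (F/T) × 1/(1 - u). With T = 100 and F = 80, the share of shocked episodes is F/T = 80.0% throughout:

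| Never converted | F/C | Excess (points) | Factor 1/(1-u) |
|---|---|---|---|
| 0 | 80/100 = 80.0% | 0.0 | 1.00 |
| 2 | 80/98 = 81.6% | 1.6 | 1.02 |
| 5 | 80/95 = 84.2% | 4.2 | 1.05 |
| 10 | 80/90 = 88.9% | 8.9 | 1.11 |
| 20 | 80/80 = 100% | 20.0 | 1.25 |

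The last row is the case in which no episode is converted after a failed first shock. Induced testing would look like this if each failed first shock were followed directly by external rescue.

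**How large might u be?** If up to five shocks were independent with per-shock success p (an assumption), u = (1 - p)^5. The excess p/(1 - u) - p is then 0.03 points at p = 80%, 0.6 at 60%, 3.4 at 40% and 9.8 at 20%. Independence is the favourable case. Section 2.0 reports a mean S-ICD defibrillation threshold of 36.6 J with a spread of 19.8 J, so patients differ, and failures within a patient may be correlated.

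**Rule in 5.5.** Assume N = 1000, one shocked episode per patient, 80% converted by the first shock and 10% never converted:

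| Patients with a shocked episode | 5.5 figure (95% exact CI) | Among those patients (95% exact CI) | Literal 3.2.1 |
|---|---|---|---|
| 100 | 80/1000 = 8.0% (6.4 to 9.9) | 80/100 = 80% (70.8 to 87.3) | 80/90 = 88.9% |
| 700 | 560/1000 = 56.0% (52.9 to 59.1) | 560/700 = 80% (76.8 to 82.9) | 560/630 = 88.9% |

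The 5.5 figure mostly reflects how many patients were tested or had an arrhythmia, and its narrow interval surrounds the wrong quantity.

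**The case against.** A reader might infer from 3.2.1 alone that the reported first-shock figure will be inflated. The documents do not support that. Section 5.5 governs the analysis of the same measure, removes no unconverted patient from the denominator, and pushes the figure the other way. Inflation follows only if the literal 3.2.1 rule is the one applied.

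The 3.2.1 wording can also be read loosely, as the percentage of episodes converted by the first shock. The two neighbouring efficacy items describe only what counts as a success and give no base. That reading is possible, but Section 7.3.2 uses successful conversion as a category distinct from failed conversion, which favours the literal one. A definition open to both still needs correcting.

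It is fair to add that complete failures are not lost from the data. Failed conversion is defined for the case report form, and induced and spontaneous conversion efficacy are listed beside the first-shock measure. That limits the harm. However, those companion measures carry the same 5.5 denominator, so as written they do not supply the missing figure.

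Finally, the size of the 3.2.1 bias rests on assumed rates and is small when few episodes go unconverted. Section 3.2.1 presents its items as data that may be reported when available, in a registry whose analysis is descriptive. All of this stands and bears on priority.

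**Conclusion.** The two sections conflict on unit and denominator, and following either as written gives a figure other than the share of shocked VT/VF episodes ended by the first shock. Read literally, 3.2.1 overstates that share by the factor 1/(1-u): about 2% in relative terms at u = 2% and 11% at u = 10%, both assumed. Section 5.5 understates it, by an amount set by how many patients were never tested or shocked: 8.0% or 56.0% against 80% in the two assumed cases. Which bias would appear in the report cannot be settled from the documents. No Registry endpoint, sample size or test depends on this measure, so it is a definition to put right before analysis and does not threaten the Registry's main results.

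**What to change.** State one definition in both 3.2.1 and 5.5; changing only one section would leave the conflict in place.

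- **Numerator:** VT/VF episodes terminated by the first S-ICD shock.
- **Denominator:** all VT/VF episodes that received at least one S-ICD shock, with never-converted and externally rescued episodes counted as first-shock failures.
- **Reporting:** induced and spontaneous episodes separately, each with the number of episodes and of patients contributing them.
- **Interval:** with episodes as the unit, replace the simple exact binomial with one that allows for several episodes per patient, for example by clustering on patient.

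The cost is a definition sentence in 3.2.1, a matching edit in 5.5 and a slightly more involved interval. The percentage may come out a little lower than under the literal 3.2.1 rule. Spontaneous shocked episodes must be classified as VT/VF or not. Section 4.4 guarantees adjudication only for endpoint-related episodes, but the analyses of appropriate and inappropriate therapy in 5.5 already need that classification, so little extra work should follow.

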4.0 Registry Design

4.1 Overview

EFFORTLESS S-ICD is an observational, prospective, non-randomized, standard of care evaluation to be conducted at approximately 50 Investigational centres worldwide where the S-ICD is approved for use and distribution.

Approximately 1000 patients currently implanted with*, or meeting eligibility criteria for the implantation of, an S-ICD System may be enrolled in the Registry. Following implant, data will be collected from each patients' scheduled and unscheduled follow-ups for at least 360 days post implant per the standard of care follow-up schedule as defined by their clinical institution. Once the 360 days of follow-up have been completed for all enrolled patients, they will continue to be followed per institutional standard of care but data will then only be collected once annually for the next 48 months. This will ensure that at least 60 months' data is available post implant on system status and clinical events.

**Retrospective enrolments meet minimal dataset requirements as described in Section 5.9*

4.2 Registry Duration

The duration, from first enrolment to Registry closure, is expected to be approximately 108 months.

4.3 Scope of Registry and Follow-Up Schedule

Patients will be followed per standard of clinical care throughout the duration of the Registry. Data will be collected from implant and all scheduled and unscheduled follow-ups up until at least 360 days of follow-up has been recorded (usually from a 12 month post-implant follow-up or closest equivalent). Subsequently data will be collected once annually for the next 48 months to ensure that a total of 60 months data post implant, is available. All complications, hospitalizations and clinical events that occur between annual follow-ups will be reported. The actual follow-up schedule is defined by the standard of care at their clinical institution.

4.4 Clinical Events and Spontaneous Episodes

At a minimum, end-point-related clinical events and end-point-related spontaneous episode data will be reviewed and adjudicated.

5.0 Statistical Methods and Analysis

The statistical analyses related to this Registry including the Sub-Study (see Appendix E) will be executed by the Boston Scientific Clinical Department and/or consultants working on behalf of Boston Scientific. All patients enrolled in the Registry will be included in the analysis. As an observational non-randomized single arm evaluation, the statistical analyses will be descriptive.

5.1 Description of Baseline Variables

Baseline demographics and clinical variables, including but not limited to relevant descriptors from the medical history, risk factors, co-morbidities, and NYHA functional class for heart failure if available, will be summarized for the cohort of patients enrolled in this Registry. Continuous variables will be summarized as means, standard deviations, medians, minimums, maximum, and interquartile ranges. Categorical variables will be summarized as frequencies and percentages. A summary of the eligibility status of enrolled patients will be performed.

